Pilot, randomized trial of the use of pediatric size phlebotomy tubes in adult critically ill patients to reduce red blood cell transfusions

NCT03286465

Version Date: 09/28/2017

Protocol Title: Pilot, randomized trial of the use of pediatric size phlebotomy tubes in adult critically ill patients to reduce red blood cell transfusions

Principal Investigator: [name] [name]

Co-Investigators: [name]; [name]; [name]; [name]

Study Coordinator: None

Population: Adult, intensive care unit patients, newly admitted to the ICU. N=200

Number of Sites: Single site / Memorial Hermann Hospital / Medical ICU, Transplant ICU

Intervention: Pediatric size phlebotomy tubes

Comparison: Adult size phlebotomy tubes

Outcomes: Primary: Time to red blood cell transfusion or hemoglobin less than 7 g/dL
Main secondary: Rate of change in hemoglobin (g/dL per patient per day)

Study Duration: 6-12 months

Subject Duration: Duration of ICU stay, up to 30 days

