The first objective of this period is to standardize the pediatric tubes phlebotomy process. Study procedures will be presented to the ICU nurses by email, printed material, and lectures. Information will include the type of pediatric tube and the blood volume needed for each test, and the importance to collect only the total estimated blood volume according to the tests that need to be performed. Pocket size cards that include the suggested volume of blood to be drawn for each pediatric tube will be provided. No guidance regarding the phlebotomy process when using adult size tubes will be given so that it reflects usual practice. The volume of fluid

drawn to clear the intravenous line will be returned to the patient in a sterile fashion in both groups whenever possible. The frequency and type of blood tests performed will follow usual practice.

The second objective of the pre-intervention period is to provide RBC transfusions recommendations to the ICU physicians. This will be accomplished by email and during any of the regular Critical Care Division meetings. An RBC transfusion will be recommended if the hemoglobin is less than 7 g/dL or if there is bleeding with associated hemodynamic instability regardless of the hemoglobin level. It will be dependent upon the ICU physician to make the final determination regarding the need of any transfusions.

Intervention period (5-11 months)

Blood tests will be collected using pediatric and adult phlebotomy tubes in the experimental and control groups, respectively (Table 1). Arterial blood gases, blood cultures, and lactate levels will be collected using the same tubes in both groups. The exposure period will be from randomization until the hemoglobin is less than 7 g/dL, an RBC transfusion order is placed, the patient is discharged from the ICU (time of an acceptance note) or dies (time of death), clinical bleeding or surgery occur, comfort care measures only are initiated, or the patient stays in the ICU for more than 30 consecutive days.

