3.5 Outcomes

Primary

The primary outcome will be the time from randomization to hemoglobin less than 7 g/dL or RBC transfusion order.

Secondary

The main secondary outcome will be the rate of change in hemoglobin (g/dL/patient/day) in the ICU. This will be calculated as the most recent hemoglobin prior to randomization minus the last hemoglobin prior to ICU discharge, death, RBC transfusion, clinical bleeding, surgery, or change of clinical status to comfort measures, divided by the number of days (rounded to the nearest 0.5) between these two values (crude estimate). If the longitudinal measures of hemoglobin levels deviate substantially from a linear trajectory, we will use a growth model to capture the best fitting function of time (see Analysis Plan for details) and generate a predicted rate of change.

Other secondary outcomes will be the proportion of participants receiving an RBC transfusion while in the ICU, the proportion of patients with at least one inadequate blood sample for laboratory analysis, and the ICU mortality. An inadequate blood sample is defined as any blood sample that requires recollection.

The patient's admission height and weight will be used to estimate the total blood volume of each patient based on Nadler's equation.¹¹ The total daily phlebotomy volume per participant will be calculated based on the number of blood tests per patient per day and the minimal blood volume for analysis of each test.

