3.7 Analysis plan

Baseline variables (e.g. gender, race, age) between groups will be examined for clinically significant differences that may have occurred by chance. If a clinically significant difference is noted, both unadjusted and adjusted analyses will be performed.

Intent-to-treat analyses will be used. The primary outcome will be assessed using time to event analysis with the Cox proportional hazard model including treatment group and ICU admission hemoglobin level group (stratifying variable). Censoring events will be death, ICU discharge, clinical bleeding, surgery, initiation of comfort care measures, and end of the study. We will report the hazard ratio and 95% confidence interval (CI).

We will assess whether the longitudinal measures of hemoglobin follow a linear trajectory. If they substantially deviate, we will employ multilevel mixed models including a quadratic term for time or splines to capture the non-linear change while accounting for within-subject correlation. We will generate predicted rates of change to compare between the study groups.

To compare the rate of change in hemoglobin (either crude or predicted) between the two study groups, a linear regression model will be used with treatment and ICU admission hemoglobin groups as covariates. Multiple regression analysis will be used to assess the relationship between the rate of change in hemoglobin as the dependent variable, and age, admission hemoglobin, acute physiology and chronic health evaluation (APACHE) II score, acute or chronic renal disease, sepsis admission diagnosis, use of medications that can cause bleeding, intervention group, and ICU admission hemoglobin group as independent variables. Proportions of RBC transfusion and proportions of at least one inadequate blood sample will be compared among the two groups using logistic regression models with treatment group and ICU admission hemoglobin level group as covariates.

Sample Size

It is estimated that the primary outcome will occur in about 20-40% of the participants in the control group.^{1,2,6,12-14} A total of 200 patients (100 in each group) will be randomized in the study. This number of participants was chosen to allow completion of the study in a reasonable time frame while obtaining preliminary information to estimate an unbiased treatment effect. This sample size allows a reasonable width of the 95% CI for the rate of the primary outcome in each group (+/- 8%).

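### The hemoglobin-slope window does not stop at hemoglobin below 7 g/dL, although the exposure period does, so untransfused patients add post-exposure values to the main secondary outcome

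*Combined protocol and SAP*

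**What the plan says.** Section 3.4 (Interventions, intervention period) defines exposure: "The exposure period will be from randomization until the hemoglobin is less than 7 g/dL, an RBC transfusion order is placed". The list goes on to ICU discharge, death, clinical bleeding, surgery and comfort care, and ends with the case where "the patient stays in the ICU for more than 30 consecutive days".

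Section 3.5 defines the main secondary outcome as a daily rate. It starts from the hemoglobin before randomization and subtracts a closing value, described as follows: "the last hemoglobin prior to ICU discharge, death, RBC transfusion, clinical bleeding, surgery, or change of clinical status to comfort measures". The result is expressed per day elapsed from the first value to the second. A positive value is therefore a decline. Hemoglobin below 7 g/dL and the 30-day limit are not in this list, and it names the transfusion rather than the order.

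Section 3.4 also says "An RBC transfusion will be recommended if the hemoglobin is less than 7 g/dL", but then: "It will be dependent upon the ICU physician to make the final determination regarding the need of any transfusions". Section 3.6 states that physicians are not blinded.

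For the primary outcome, section 3.7 says: "Censoring events will be death, ICU discharge, clinical bleeding, surgery, initiation of comfort care measures, and end of the study". The synopsis gives "Subject Duration: Duration of ICU stay, up to 30 days".

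**The concern.** The slope window already stops at transfusion, bleeding, surgery and comfort care, so it is built as a measure of change during exposure. Hemoglobin below 7 g/dL is the one clinical event that ends exposure without ending the window. Because transfusion is recommended and not automatic, a patient can cross 7 g/dL, finish exposure, remain untransfused in the ICU, and have a later value taken as the last hemoglobin.

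Three things are at stake.
- Crossers tend to be fast decliners. Averaging in days after the crossing can lower their slopes, and more controls should cross if the tubes work.
- The length of the window depends on a decision made by someone who knows the allocation.
- Two analysts, one following section 3.4 and one following section 3.5, would compute different slopes for the same patient. Neither section 3.5 nor section 3.7 says which values enter the growth model. Section 2.2 makes the rate in each group an objective, so the arm-level rates matter as well as their difference.

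**Working it through.** **Plan's own figure.** There is none for the slope: no effect, SD, power, length of stay or delay to transfusion is given. The usable design inputs are 100 patients per arm and a control event rate of 20–40% (section 3.7). Everything else below is assumed.

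**Step 1. One patient (illustrative values).** Hemoglobin goes from 9.0 to 6.8 g/dL in 4 days, and the untransfused patient is at 7.4 g/dL on day 10.
- Window stopped at the crossing: (9.0 − 6.8)/4 = 0.55 g/dL/day.
- Window as written: (9.0 − 7.4)/10 = 0.16 g/dL/day.

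**Step 2. Mechanism.** Let w be the share of the window after the crossing, s the rate of decline before it and s′ the rate after it. Then

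written slope = (1 − w)·s + w·s′.

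Step 1 checks: 0.4 × 0.55 + 0.6 × (−0.10) = 0.16.

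With a the share of an arm affected (C control, P pediatric) and D the between-arm difference, using averages,

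D(written) ≈ D(aligned) − a_C·w_C·(s_C − s′_C) + a_P·w_P·(s_P − s′_P).

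- *Decline continues at each patient's usual-care rate.* The control term is zero. The pediatric arm loses the tube effect for part of its window, and the proportional loss is about a_P·w_P.
- *Hemoglobin flat afterwards.* Both arms are diluted, the control arm more if more controls cross and decline faster. D shrinks.
- *Hemoglobin falls faster afterwards.* D widens if a_C·w_C·(s′_C − s_C) exceeds the same product in the pediatric arm.

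**Step 3. Simple range for the first case.** Loss = share crossing × share of crossers untransfused × share of window after crossing. The 20–40% control rate serves as a generous value for the share crossing, since it also counts transfusion orders placed above 7 g/dL.
- Low: 0.20 × 0.10 × 0.10 = 0.2%.
- High: 0.40 × 0.50 × 0.50 = 10%.
- Extreme, nobody transfused: 0.40 × 1 × 0.50 = 20%.

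**Step 4. Simulation, lower event rate.** 60,000 patients per arm; admission hemoglobin uniform from 7.2 to 14 g/dL; decline 0.15 g/dL/day (SD 0.15); tube effect 0.06 g/dL/day; mean stay 6 days; measurement SD 0.3 g/dL; average rate after crossing 0.15, 0 or −0.10 g/dL/day. Simulated crossing was about 15% (control) and 11% (pediatric).

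| Values below 7 g/dL followed by prompt transfusion | Written difference ÷ aligned difference |
|---|---|
| 90% | 0.99 |
| 50% | 0.94–0.97 |
| 10% | 0.87–0.93 |

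The loss is 1–13%. In the worst row the difference falls from 0.0616 to 0.0537, that is by 0.0079 g/dL/day. With a slope SD of about 0.26, the standard error at 100 per arm is √(2 × 0.26²/100) = 0.037, so the loss is about 0.2 standard errors. This run let the written window pass day 30, which touches only e^(−30/6) = 0.7% of stays.

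**Step 5. Simulation at the plan's event rate.** Step 4 lies below the plan's 20–40%. With decline 0.20–0.30 g/dL/day (SD 80% of the mean), 30% slower decline with pediatric tubes, mean stay 7–8 days and 10–50% of crossers untransfused, control crossing was 20–33%. The difference shrank by 2–14% if hemoglobin was flat afterwards and by 1–7% if it continued at the usual-care rate. A wider set of assumed inputs, with control crossing 21–41%, gave 1–18%: mostly below 10%, and 1–3% when 10% were untransfused. The ends are approximate and move by a few points with the assumed decline and stay.

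**Step 6. Cost of the aligned window.** Stopping at the first value below 7 g/dL selects low readings. With measurement SD 0.3 g/dL (assumed), this inflated the difference by about 3–4%.

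**The case against.** The strongest defence is that section 3.7 specifies intention to treat and section 3.5 describes change in the ICU, so time after exposure is not in itself an error. That would be convincing if the window ran to ICU discharge for everyone. It does not: it stops at four other clinical events that end exposure, and nothing explains why this one is left out.

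It is also fair to say that the affected group is narrow. Most patients below 7 g/dL should be transfused under the recommendation, which closes the window anyway. The untransfused share has no source in the documents, the outcome is secondary in a pilot, and the aligned window has its own bias. All of this stands, and it limits the size of the point.

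Four stronger readings are tempting and are not supported.
- *Bias from days beyond day 30.* The synopsis caps each participant at 30 days, so later follow-up is not planned. The silence of sections 3.5 and 3.7 is a gap in wording.
- *Off-assignment time mainly in the control arm.* Adult tubes are usual practice. If patients return to usual practice, controls stay on their assigned tubes and only pediatric-arm patients can be truly off-assignment. Dilution in the control arm would come from a changed trajectory after crossing.
- *Assigned tubes certainly stop.* This is inferred from the term exposure period. No section says which tubes follow. Section 4 keeps participants in their assigned group for the whole trial, but in the context of crossover.
- *The difference must shrink.* It did in every scenario run, but Step 2 shows when it would widen.

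**Conclusion.** The mismatch is real and sits in the definition of the main secondary outcome. Under assumed inputs it can shrink the between-arm difference in slope by about 1–3% if 10% of patients crossing 7 g/dL are untransfused, and by up to about 18% if 50% are and hemoglobin then stays flat. The size depends on the untransfused share, the time spent in the ICU after crossing and the later trajectory, none of which the documents give. The primary outcome is unaffected, because hemoglobin below 7 g/dL is itself an event there. This is a worthwhile, inexpensive correction and does not threaten the trial's main result.

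**What to change.** In section 3.5, end the slope window at the end of the exposure period as section 3.4 defines it, for both the crude estimate and the growth model. When hemoglobin below 7 g/dL ends exposure, take that first value as the last one. Use the transfusion order, not the transfusion, in both sections.

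Report the window as now written as a sensitivity analysis, because of the inflation in Step 6. State in the protocol which tubes are used after exposure ends, so that the two windows can be interpreted.

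Repeat the synopsis's 30-day limit in sections 3.5 and 3.7, as a wording correction only.

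The cost is a few phrases and one extra run of a planned model. No additional data are needed.

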3.2 Participants

Inclusion (all of the following)

- Age \geq 18 years old
- New admission to the medical or transplant ICU at Memorial Hermann Hospital in Houston
- ICU admission hemoglobin level of at least 7 g/dL. The ICU admission hemoglobin will be the most recent hemoglobin value available at the time of screening for inclusion in the study.
- Randomization is expected within 12 hour of admission to the ICU

Exclusion (any of the following)

Conditions that affect the generation or loss of RBCs

- Clinical bleeding. Defined as menstrual bleeding, bleeding leading to a change in the frequency of hemoglobin monitoring or to an order for a medication, transfusion, procedure, or consultation intended to prevent or treat bleeding.
- Known hemolytic disorder (e.g. sickle cell disease, hereditary spherocytosis, autoimmune hemolytic anemia)
- Bone marrow disorder (e.g. aplastic anemia, marrow infiltration disorder, chemotherapy within the last 8 weeks)

Randomization to adult size phlebotomy tubes is not recommended

- Jehovah's Witnesses

Collection of blood tests is not possible or desired

- Patient is comfort care measures only

Inability to complete the desired time of follow up

- Refractory shock: mean arterial blood pressure below 60 mmHg despite maximal doses of 3 vasopressors. Maximal dose of vasopressors are as follows: Norepinephrine 70 mcg/min; vasopressin 0.04 units/min; epinephrine 35 mcg/min; dopamine 20 mcg/kg/min; phenylephrine 350 mcg/min
- Severe acidosis: pH below 7 in more than one arterial blood gas within 24 hours of ICU admission in the absence of diabetic ketoacidosis

Other

- Surgical admission diagnosis
- Pregnancy
- Current prisoner

33 Allocation

All patients admitted to the medical or transplant ICU will be screened for eligibility. Group assignment will be done using the randomization module in the Research electronic data capture (RedCap). Randomization will be stratified by ICU admission hemoglobin level (7 to 9.49 g/dL, 9.5 to 11.99 g/dL, and 12 g/dL or greater). Patients will be randomized using permuted blocks of 4 or 6 and a 1 to 1 ratio, into one of two groups: the pediatric size phlebotomy tubes group or the adult size phlebotomy tubes group.

34 Interventions

Pre-intervention period (1 month)

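### The crude hemoglobin rate is undefined for intervals under 6 hours and, entered unweighted, gives short intervals disproportionate influence, at a cost in precision

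*Combined protocol and SAP*

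**What the plan says.** Section 3.5 states: "The main secondary outcome will be the rate of change in hemoglobin (g/dL/patient/day) in the ICU". The numerator is "the most recent hemoglobin prior to randomization minus the last hemoglobin prior to ICU discharge, death, RBC transfusion, clinical bleeding, surgery" or the change to comfort measures. That difference is then "divided by the number of days (rounded to the nearest 0.5) between these two values (crude estimate". No minimum interval is set. No rule covers a denominator that rounds to zero or a patient with no hemoglobin after randomization.

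Section 3.7 compares the groups as follows: "To compare the rate of change in hemoglobin (either crude or predicted) between the two study groups, a linear regression model will be used". The covariates are treatment and hemoglobin group, and no weights are mentioned.

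There is an alternative branch. Section 3.5 says: "If the longitudinal measures of hemoglobin levels deviate substantially from a linear trajectory, we will use a growth model". Section 3.7 adds: "we will employ multilevel mixed models including a quadratic term for time or splines to capture the non-linear change". Predicted rates then replace the crude ones. The trigger is departure from linearity only, and no threshold is given for it. Under a linear trajectory the crude rate is what gets analyzed.

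Section 3.2 sets no minimum ICU stay, and section 3.4 leaves blood-test frequency to usual practice.

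**The concern.** Two separate problems sit in one formula.

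The first is definitional. Rounding to half-days turns a short interval into zero and the rate into a division by zero. A patient whose last value is the pre-randomization value gives 0/0. Section 3.7 calls for intent-to-treat analyses, yet such patients would leave the comparison through a rounding rule. They could include someone transfused within hours.

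The second is statistical. A difference between two single measurements has the same measurement noise whatever the time between them. Dividing by a short time magnifies that noise, and ordinary regression then treats a half-day rate and a 20-day rate as equally informative.

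Estimating the rate of change in each group is a stated secondary objective (section 2.2). Section 1 also criticizes earlier trials for not relating hemoglobin change to time at risk. The trial therefore has its own reason to handle time carefully.

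**Working it through.** **No figure to reproduce.** The documents give no SD, effect size, precision or power for this outcome.

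**Rounding (no assumptions needed).**
- Below 0.25 day (6 h), the interval rounds to 0 and the rate is undefined. Exactly 6 h is a tie with no rule.
- From 6 to 18 h, the interval becomes 0.5 day. True/rounded runs from 6/12 = 0.5 to 18/12 = 1.5, and the reported rate is the true rate times this ratio.
- From 18 to 30 h, it becomes 1 day, with ratio 18/24 = 0.75 to 30/24 = 1.25.

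**Noise.** Let σ be the SD of a single hemoglobin about its trend, taken as constant, and T the interval. The noise variance of the rate is 2σ²/T². Comparing T = 0.5 with T = 5 days gives (5/0.5)² = 100 for any σ. With an assumed σ of 0.3 g/dL, the noise SD is √2 × 0.3/T: 0.85 g/dL/day at 0.5 day, 0.42 at 1 day and 0.085 at 5 days.

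True differences in slope between patients (SD τ) narrow the contrast in total variance. With τ = 0.25 it is (0.0625 + 0.72)/(0.0625 + 0.0072), about 11 rather than 100.

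**Size.** None of the following inputs is in the documents. Intervals are log-normal, capped at 30 days; σ = 0.4 g/dL; τ = 0.25 g/dL/day; mean decline 0.3 g/dL/day. The crude rate is (slope × true interval + noise)/rounded interval. The benchmark weights each patient by inverse variance. The standard error (SE) of the group difference is SD × √(2/100).

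| Median interval (log-SD) | Undefined | Patients under 1 day | Their share of variance | Their share of information | SD, unweighted / weighted | SE, unweighted / weighted | Excess SE |
|---|---|---|---|---|---|---|---|
| 2 d (0.9) | about 1% | 21% | 64% | 3.9% | 0.567 / 0.367 | 0.080 / 0.052 | about 55% |
| 3 d (0.9) | 0.3% | 11% | 47% | 1.7% | 0.457 / 0.325 | 0.065 / 0.046 | 41% |
| 4 d (0.8) | 0.03% | 4% | 24% | 0.6% | 0.369 / 0.302 | 0.052 / 0.043 | 22% |

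Of 200 patients, the undefined rates are about 2, 0.6 and 0.06.

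**Varying σ and τ.**
- Median 3 days, log-SD 0.9: the excess is about 26% at σ 0.3 and τ 0.25, 12% at σ 0.2 and τ 0.25, and 11% at σ 0.3 and τ 0.4.
- Log-SD 0.7, σ 0.3, τ 0.3: about 11% at a median of 3 days and 6% at 4 days.
- The most favorable corner of these ranges (median 4 days, log-SD 0.8, σ 0.2, τ 0.4) gives SDs of 0.425 and 0.415, an excess of about 2%. So 6% is the low end of the listed combinations, not a floor.

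A wider grid used medians of 2 to 5 days, log-SD 0.7 to 1.0, σ 0.2 to 0.5 and τ 0.1 to 0.5, in 54 combinations. The relative efficiency of the unweighted analysis ran from 0.13 to 0.99. Intervals that round to 1 day or less supplied 4% to 85% of the variance, clearly more than half in 22 combinations and about half in 2 more.

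**Rounding against weighting.** With exact times but still no weights, the SD is 0.587 against 0.567 rounded at a median of 2 days, 0.462 against 0.459 at 3 days, and 0.362 against 0.368 at 4 days. Removing the rounding alone gains essentially no precision.

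**The case against.** A reader might infer that the shortest stays dominate the outcome. The documents do not support that, because they give no stay distribution, hemoglobin noise or slope variation. Even under the assumptions in the table, the variance share passes half in only one of three scenarios.

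Undefined rates should be rare. The interval starts at the hemoglobin before randomization, so it is longer than follow-up itself. That "Randomization is expected within 12 hour of admission to the ICU" does not show intervals to be short. Section 3.2 also excludes several groups likely to have very brief follow-up, such as refractory shock and comfort care. This stands: the defect is certain in the formula but touches few patients.

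The crude rate is not always used, since a non-linear trajectory brings in the mixed model. This stands as a limit on scope. It is not a cure, because a linear trajectory does nothing for a zero denominator or for short-interval noise.

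Equal weighting is also a legitimate estimand, the mean of patient rates, and does not by itself bias a randomized comparison. The weighted benchmark assumes that slope is independent of interval length and that variances are known. Here follow-up can end because hemoglobin fell, so the benchmark is a best case. Both points stand and limit the claim to precision.

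Finally, this is a secondary outcome in a pilot that makes no power claim for it. That lowers the stakes, but the repair is cheap.

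**Conclusion.** The point holds in a limited form, for the crude branch only. Two parts need no outside figures: the rate is undefined below 6 hours, with distortion by a ratio of 0.5 to 1.5 between 6 and 18 hours; and rates whose noise variance differs 100-fold between half a day and 5 days are weighted equally.

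The loss of precision is conditional. In the combinations worked, with assumed medians of 2 to 4 days, σ 0.2 to 0.4 g/dL and τ 0.25 to 0.4 g/dL/day, the standard error is roughly 6% to 55% larger than the best-case benchmark, and nearer 2% at the most favorable corner.

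The documents do not support reading this as a biased treatment comparison or as a large loss from the intent-to-treat set. The primary Cox analysis does not use this rate and is unaffected.

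**What to change.** In section 3.5, delete the rounding and compute time from exact collection times.

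In section 3.7, make the main secondary comparison a treatment-by-time contrast in one mixed model of all hemoglobin values in the window that section 3.5 already defines. Include a random intercept and slope, and hemoglobin group as covariate. Use it whether or not the trajectory is linear. If it is not, add quadratic or spline time and fix in advance the time at which the contrast is read. Short-interval patients then contribute according to their information, without ad hoc weighting by length of stay.

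Keep the two-point rate as a descriptive summary for patients with at least 24 hours between values. Patients with no hemoglobin after randomization add essentially nothing to the slope contrast under any model, so count and report them by group.

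The cost is wording in two sections, plus extracting and modelling all hemoglobin values rather than two per patient. The plan already foresees serial values and mixed models. One real change should be acknowledged: the estimate is no longer the equally weighted mean of patient rates.

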7. DATA COLLECTION AND DATABASE MANAGEMENT

6.1 Data collection

The investigators will fill out the blood tests form to document the number of blood tests performed and the occurrence of insufficient samples or crossover between interventions. This will be done through review of the electronic medical record and interview of the nurses. This information and data obtained from the patient's electronic medical record will be entered directly in the RedCap database, a secure electronic database (Appendix).

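### The inadequate-sample outcome takes no account of how many samples each patient gives; if counted only during exposure, tubes that work could show a modest false excess

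*Combined protocol and SAP*

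**What the plan says.** Section 3.5 (Outcomes, Secondary) includes "the proportion of patients with at least one inadequate blood sample for laboratory analysis" and adds: "An inadequate blood sample is defined as any blood sample that requires recollection". It gives no start or end for the counting.

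Section 3.7 (Analysis plan) states that "proportions of at least one inadequate blood sample will be compared among the two groups using logistic regression models". The covariates are treatment group and admission hemoglobin group. Neither the number of samples nor the time at risk enters the model, and no per-sample comparison is planned.

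Section 3.4 (Interventions, Intervention period) defines when the assigned tubes are in use: "The exposure period will be from randomization until the hemoglobin is less than 7 g/dL, an RBC transfusion order is placed". Other exits follow, including ICU discharge, death and the case where "the patient stays in the ICU for more than 30 consecutive days".

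On data, section 6.1 (Data collection) has the investigators "document the number of blood tests performed and the occurrence of insufficient samples".

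**The concern.** A yes/no outcome of this kind depends on two things: how often a sample fails, and how many samples the patient gives. Only the first describes the tubes. Randomization balances patients at baseline, but the number of samples arises afterwards. Two of the events that end exposure are the components of the primary outcome. If pediatric tubes delay those events, that arm stays exposed longer and is drawn more often. More of its patients would then have at least one recollection even if each draw were equally likely to succeed.

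Feasibility of pediatric tubes in an adult ICU is a stated objective (section 2.2), and section 4 names insufficient blood requiring recollection as a potential adverse event. A spurious excess here could count against an intervention that works. A genuine improvement in sample adequacy could be partly hidden.

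**Working it through.** **Plan's own figure.** The plan gives no precision or power figure for this outcome. Its only one, +/- 8% (section 3.7), concerns the primary outcome. It reproduces at a 20% rate, 1.96 × √(0.2 × 0.8/100) = 7.8%, and has no bearing on this point.

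**Inputs from the protocol.** 100 patients per group; control primary-event proportion p = 20-40%.

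**Assumed, because the documents give none.** Hazard ratio HR; mean control exposure 5 days; 4 samples per day (20 per control patient); control per-sample inadequate rate 0.5% to 5%; two-sided 5% test. The mean number of inadequate samples per control patient is then m = 20 × rate = 0.1 to 1. Counting is taken to be limited to the exposure period.

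**Formulas.** Exits are exponential with competing causes, ignoring the 30-day cap. If a share p of control exits are primary events and treatment multiplies that hazard by HR:

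- exposure ratio (pediatric/control) = 1/(1 − p(1 − HR))
- P(at least one), control = m/(m + 1)
- P(at least one), pediatric, same per-sample rate = m/(m + 1 − p(1 − HR))

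**Worked case at the upper end.** p = 0.40, HR = 0.5, m = 0.5: control 0.5/1.5 = 33.3%; pediatric 0.5/1.3 = 38.5%; excess 5.1 points. The standard error of the difference is √(0.333 × 0.667/100 + 0.385 × 0.615/100) = 6.8 points. The chance of a nominally significant result is P(Z > 1.96 − 0.76) + P(Z < −1.96 − 0.76), about 12%.

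**Range, equal per-sample rates, m = 0.1 to 1.**

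| Control events | HR | Exposure ratio | False excess (points) | False-positive rate |
|---|---|---|---|---|
| any | 1 | 1.00 | 0 | 5% |
| 20% | 0.7 | 1.06 | 0.5-1.5 | 5.2-5.5% |
| 30% | 0.5 | 1.18 | 1.4-4.1 | 6.3-8.8% |
| 40% | 0.5 | 1.25 | 2.0-5.6 | 7.6-12.3% |
| 40% | 0.3 (extreme) | 1.39 | 3.1-8.1 | 10.9-21.1% |

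**When the per-sample rate truly differs.** Take p = 0.30, HR = 0.5, control rate 1% (m = 0.2, control 16.7%).

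- Rate halved: pediatric 0.1/0.95 = 10.5%, against 0.1/1.1 = 9.1% had exposure been equal. Longer exposure hides part of the reduction. Simulated power is 27% (binary) against 52% (per-sample).
- Rate raised 1.5-fold: pediatric 0.3/1.15 = 26.1%, against 0.3/1.3 = 23.1%. Longer exposure inflates the increase. Simulated power is 38% (binary) against 32% (per-sample).

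**Power for a true doubling, equal exposure** (simulation, 100 per group, not adjusted for hemoglobin group; binary against per-sample with patient-clustered variance):

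| Control rate | No clustering | Clustering, ICC 0.02 |
|---|---|---|
| 0.5% | 39% vs 46% | 33% vs 33% |
| 1% | 56% vs 76% | 52% vs 53% |
| 2% | 69% vs 97% | 70% vs 82% |
| 5% | 73% vs 100% | 80% vs 100% |

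Under equal rates the per-sample analysis rejects in 4-6% of trials with no or mild clustering, and in up to about 7.5% with strong clustering and sparse events.

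**The case against.** **The bias needs an unstated window.** Early stopping at the primary event matters only if counting stops there too. Over the whole ICU stay this route to bias closes, although the outcome would still depend on length of stay and would take in samples drawn after the assigned-tube period. This objection stands, and the finding is conditional on it. Section 5, where a blinded investigator decides when each participant has met the completion criteria, fits counting within exposure better but does not settle it.

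**The effect is small.** For most of the range the false-positive rate stays close to 5%. The trial is a pilot meant to estimate effects, and no test level is stated. This also stands.

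**The outcome is legitimate as it is.** The share of patients needing a recollection measures patient burden at the unit of randomization. That is right, and it is a reason to keep it. It does not isolate how the tubes perform.

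**Power.** A reader might infer that the binary outcome generally misses differences a per-sample rate would find. The documents do not support that: they give no failure rate, only that earlier adult studies showed no difference (section 4). The gain vanishes when failures are rare and cluster within patients. If pediatric tubes are worse, longer exposure adds to the binary signal, though part of that signal is then exposure rather than tube performance.

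**Conclusion.** The point holds in a limited form. The outcome depends on how many samples each patient has, and the planned model ignores that. If counting is confined to the exposure period, effective tubes can produce a false excess of about 0.5 to 6 percentage points for HR 0.5-0.7 across the protocol's 20-40% event range. The false-positive rate is then about 5% to 12%. The 12% belongs to the corner with 40% events, HR 0.5 and frequent failures, and should not be read as typical. At HR 1 there is no bias. A per-sample analysis is clearly more powerful when inadequate samples are frequent, and gains little when they are rare or cluster within patients. The hazard ratio, exposure length, samples per day, failure rates and clustering are all assumptions.

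A reader might also take this to be the trial's main feasibility and safety measure. Section 3.5 places it among the other secondary outcomes, and section 2.2 also names recruitment. The change is worth making because it is cheap and serves a stated objective. The primary result is not affected.

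**What to change.** 1. In section 3.5, state that inadequate samples are counted during the assigned-tube exposure period.
2. In section 3.7, add a between-arm comparison of inadequate samples per sample collected. Use a count model (Poisson or negative binomial) with the log number of samples as offset, patient-clustered or overdispersed variance, and treatment and hemoglobin group as covariates.
3. Report it alongside the per-patient proportion, which stays as a measure of patient burden.
4. Define the denominator. Section 6.1 records the number of blood tests, which may not equal the number of samples, and the form itself is not shown. Confirm that samples collected can be derived from it. Say also whether blood gases, cultures and lactate, which use the same tubes in both groups, are included.

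The cost is plan wording, a little more analysis, and the check on the form. If the form yields the number of samples, no new data are needed.
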